4.2 Number of Patients

Enrolled number : **140**

Failed during screening : **10**

Drop-out number : **28**

Estimated evaluable number : **112** (experimental group 56, control group 56)

4.3 Schedule of Activities

Time-Event scheme(評估時程表):

Phase	Screening	Treatment					Follow-up	
Day	0	0	7	14	21	28	56	84
Clinic visit	X	X	X	X	X	X	X	X
Screening/administration/safety								
ICF/assent form	X							
Inclusion/Exclusion criteria	X							
Medical and surgical history	X							
Lab exam	X							
MRI or ABR exam	X							
Randomization/Administration								
Randomization	X							
Administration of study drug	X	X	X	X	X	X		
Efficacy/Safety								
Symptoms			X	X	X	X	X	
Audiometry	X						X	X

The physician confirm that the patient meets the inclusion criteria at the initial visit (day 0). Then the patients would be asked if he/she is willing to participate into this clinical trial. If the patient agreed, then medical history taking, audiometry and lab examination, MRI or ABR examination will be arranged at same time. He/she will be randomized into either experimental arm or control arm. The treatment will be started immediately. The blood test will be performed at first visit and the data will be checked at day 7. Patients in both arms would follow up at our clinic at day 7,14,21,28,56, and 84. Pure tone audiometry and speech audiometry will be followed at day 56 and 84. Symptoms and adverse effects (safety monitoring) will be followed up at day 7,14,21,28, and 56.

5. Study Population

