- 2. Previous middle ear disorder such as chronic otitis media, or previous ear surgery
- 3. Meniere's disease and fluctuating hearing loss patients
- 4. Pregnancy or trying to become pregnant
- 5. Leukemia, hemodialysis, and patients who received chemotherapy before.
- 6. Previous head and neck radiotherapy
- 7. Cerebellopontine (CP) angle tumor such as vestibular schwannoma
- 8. Patients with moderate to severe hepatic insufficiency
- 9. Patients with major depression disorder or suicide attempt
- 10. Patients with glaucoma

Study Procedures :

1. Expected inclusion patient number (enrolled number: **140**; evaluable number: **112**)
The participants would be divided into two group, half in the experimental group and the other half in the control group.
2. All patients will receive audiology examination, laboratory examination, magnetic resonance imaging of brain or auditory brainstem response at the first visit. Then the patient would be followed at the clinic weekly till the sixth week. Audiology examination will be arranged during the first week and then monthly till 12 weeks.
3. As for the treatment, the control group will receive systemic steroid with/without intratympanic steroid for 2 weeks as the standard therapy for sudden sensorineural hearing loss. The experimental group will receive systemic steroid with/without intratympanic steroid for 2 weeks and simultaneously oral topiramate for 6 weeks.
4. There will be no specimen collection in this study.
5. The patients' gender, age, initial and final hearing threshold, laboratory examination result, audiology result and symptoms will be collected.

Concomitant Treatments : not applicable

1. Concomitant Therapy : Prescribe systemic steroid with/without intratympanic steroid
2. Prohibited Therapy : nil

Statistical Methods :

1. Main study Hypothesis : Equality Superiority Non-inferiority
 Equivalence Other _____
2. Estimated Sample Size : Anticipated enrolled size 140 , Estimated evaluable number 112
Anticipated enrolled size in our center 45 , Estimated evaluable number in our center 40

Protocol: The role of migraine prophylaxis agent topiramate in treating patients with migraine and sudden sensorineural hearing loss

Version: 6

Date: 20220812

PASS 15.0.13

2022/8/2 下午 02:01:50

Two-Sample T-Tests Assuming Equal Variance

Numeric Results for Two-Sample T-Test Assuming Equal Variance

Alternative Hypothesis: $H1: \delta = \mu_1 - \mu_2 \neq 0$

Target Power	Actual Power	N1	N2	N	μ_1	μ_2	δ	σ	Alpha

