5.2 Exclusion Criteria

Exclusion criteria:

- (1) Previous SSNHL history
- (2) Previous middle ear disorder such as chronic otitis media, or previous ear surgery
- (3) Meniere's disease and fluctuating hearing loss patients
- (4) Pregnancy or trying to become pregnant
- (5) Leukemia, hemodialysis, and patients who received chemotherapy before.
- (6) Previous head and neck radiotherapy
- (7) CP angle tumor such as vestibular schwannoma
- (8) Patients with moderate to severe hepatic insufficiency
- (9) Patients with major depression disorder or suicide attempt
- (10) Patients with glaucoma

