5.3 Withdrawal criteria

Withdraw from the study:

Participants of this study can withdraw from this study at any time when the patient disagree the consent, or had intolerable adverse effects after medication, or could not follow the treatment protocol.

The data of the withdraw patients will be excluded from the audiology analysis. The reason of withdrawal would be analyzed and reported.

6. Treatments

6.1.Treatment Administration

Both experimental group and control group will receive systemic steroid with/without intratympanic steroid as the standard treatment for sudden sensorineural hearing loss. The total duration of systemic steroid is 2 weeks.

As for the experimental group, topiramate 25 mg orally before bedtime with weekly escalation of 25 mg up to 100 mg. More specifically, the patient will receive 25mg daily at first week. Then the dose will be titrated up to 50mg in the second week, 75mg in the third week, and 100mg daily during the 4-6 weeks.

The dose of topiramate will be half in patients with renal insufficiency ($\text{Cl}_{\text{CR}} \leq 70 \text{ mL/min}$).

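### The day-0 blood results are scheduled to be checked only at day 7, so nothing requires creatinine clearance to be known before the first topiramate dose, and the half-dose rule can be missed in week 1

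*Protocol*

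**What the plan says.** Protocol section 4.3 places the whole start of the trial on day 0: consent, history, audiometry, laboratory tests, imaging or brainstem response, and randomisation. It then says "The treatment will be started immediately". On the blood results it says "The blood test will be performed at first visit and the data will be checked at day 7". The schedule table in the same section marks the laboratory examination, randomisation and study drug all on day 0. The synopsis (Study Procedures) agrees on when the tests are done: "All patients will receive audiology examination, laboratory examination, magnetic resonance imaging of brain or auditory brainstem response at the first visit". It also has topiramate given at the same time as the steroid.

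Section 6.1 sets the dose. In week 1 "the patient will receive 25mg daily at first week", and the dose is then "titrated up to 50mg in the second week, 75mg in the third week, and 100mg daily during the 4-6 weeks". The renal rule follows: "The dose of topiramate will be half in patients with renal insufficiency", defined there as a creatinine clearance of 70 mL/min or less. The rule has no start date or grace period.

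The only renal entry among the exclusions in section 5.2 is dialysis, within the item "Leukemia, hemodialysis, and patients who received chemotherapy before".

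**The concern.** A dose rule with a numeric laboratory threshold needs the laboratory value before the first dose. Section 6.1 states such a rule, and section 4.3 schedules the look at its input a week after dosing begins. Patients with renal insufficiency short of dialysis are eligible, so the half-dose rule is the only renal safeguard the protocol names for them.

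If the insufficiency is known from the day-0 history, the dose can be halved from the first tablet. If it would first appear in the day-0 bloods, nothing in the text makes anyone look in time, and the patient starts on the unadjusted dose. What is at stake is adherence to the protocol's own dosing rule, and some extra drug in patients the protocol has singled out for less. Power, the primary endpoint and the comparison of arms are not at issue.

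**Working it through.** The protocol states no figure on this point, so there is none to reproduce. The check sets the two sections side by side and then sizes the gap.

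**Order of events**

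| Step | Time | Source |
|---|---|---|
| History, blood draw, randomisation | day 0 | 4.3, text and table |
| First topiramate dose | day 0 | 4.3, text and table |
| Blood results checked | day 7 | 4.3, text |
| First escalation, to 50 mg (25 mg if halved) | start of week 2 | 6.1 |

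The check falls after seven days of dosing and at the point of the first escalation.

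**Inputs for the dose arithmetic (6.1):** 25, 50 and 75 mg/day in weeks 1, 2 and 3, then 100 mg/day in weeks 4 to 6 (21 days). Halving is taken to apply to every step.

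**Total dose = sum of (days × daily dose)**

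- Full schedule: 7×25 + 7×50 + 7×75 + 21×100 = 175 + 350 + 525 + 2100 = 3150 mg.
- Halved from the first dose, as the 6.1 rule gives: 7×12.5 + 7×25 + 7×37.5 + 21×50 = 87.5 + 175 + 262.5 + 1050 = 1575 mg.
- Halved only after the day-7 check, as 4.3 is scheduled: 7×25 + 7×25 + 7×37.5 + 21×50 = 175 + 175 + 262.5 + 1050 = 1662.5 mg.

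**Excess**

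- Week 1: 175 − 87.5 = 87.5 mg, or 12.5 mg/day. This is twice the dose the rule gives for that week.
- Whole course: 1662.5 − 1575 = 87.5 mg, and 87.5 / 1575 = 5.6%.
- Highest daily dose: 50 mg in both cases.

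**Who is exposed:** only the experimental arm, 140 / 2 = 70 patients, and within it only those with a clearance of 70 mL/min or less that is not known at day 0. The protocol gives no figure for that fraction.

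**The case against.** The best defence is that the sequence is a reasonable one. Treatment of sudden hearing loss starts at once, topiramate begins at its lowest step, and the bloods are read before any increase. The unadjusted week-1 dose of 25 mg is what a patient on the halved schedule would take in week 2 anyway. Symptoms and adverse effects are also reviewed at day 7, and intolerable effects are a ground for withdrawal under section 5.3. All of this stands, and it is why the point is small. It does not make the rule in 6.1 workable in week 1.

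Four stronger readings are tempting, and the protocol does not support them:

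- *That the rule cannot be applied in week 1.* Section 4.3 says when the results will be checked; it does not forbid looking sooner. The accurate statement is that an earlier look is not required.
- *That these patients run through the course at full dose.* The day-7 check allows every later step to be halved.
- *That patients who meet the hepatic exclusion will be randomised and dosed.* The exclusion reads "Patients with moderate to severe hepatic insufficiency" and names no laboratory criterion, and the protocol does not say that liver tests are in the panel.
- *That a sizeable number of patients is affected.* The protocol has no data on this, and any count would be a guess.

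The laboratory examination does sit in the screening column of the schedule table, which might suggest that it is read at screening. Randomisation sits in the same column, however, and the text gives day 7 for the reading.

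**Conclusion.** The point holds as a minor dosing-safety gap. As scheduled, the half-dose rule is not applied in week 1 to eligible experimental-arm patients whose renal insufficiency is not known from history. Each of them takes 25 instead of 12.5 mg/day for seven days, 5.6% more than the halved course, and never goes above the halved maximum.

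The conclusion rests on three assumptions:

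- The panel includes creatinine. The protocol names no analytes. If creatinine is not in the panel, the 6.1 rule has no scheduled input at all.
- The staff follow the day-7 timing as written.
- The result is acted on at the day-7 visit, before the first escalation.

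**What to change.** In section 4.3, replace the clause about checking the results at day 7 with: *creatinine clearance from the day-0 blood test will be read before the first topiramate dose, and the section 6.1 dose rule applied from that dose; systemic steroid starts at once in both arms.* State in the same place that the panel includes creatinine.

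Two other places need to agree with this. The immediate start in 4.3 should be tied to the steroid, and the synopsis wording that has topiramate begin together with the steroid should allow for the wait.

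The renal check only sets a dose, so it may follow randomisation. A laboratory result used to decide eligibility is different: it should be read before randomisation in both arms. Tying it to the first topiramate dose would set a deadline in one arm only and could lead to exclusions after randomisation in that arm alone.

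The cost is a few wording changes and a short delay to topiramate in the experimental arm. Section 6.1 gives the drug at bedtime, so a same-day result would mean no delay. The blood is already drawn on day 0. If creatinine is not in the panel, it is one added test on that sample. No extra patients or visits are needed.

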5.1 Inclusion Criteria

Inclusion criteria:

- (1) Age > 20

- (2) Confirmed diagnosis of unilateral sudden sensorineural hearing loss(SSNHL)
- (3) Treatment started 14 days within onset of SSNHL

The diagnostic criteria of SSNHL:

A subset of sudden hearing loss that (a) is sensorineural in nature, (b) occurs within a 72-hour window, and (c) consists of a decrease in hearing of ≥ 30 decibels affecting at least 3 consecutive frequencies.

The diagnostic criteria of vestibular migraine:

- A. At least 5 episodes with vestibular symptoms of moderate or severe intensity, lasting 5 min to 72 hours
- B. Current or previous history of migraine with or without aura according to the International Classification of Headache Disorders (ICHD)
- C. One or more migraine features with at least 50% of the vestibular episodes:
 - headache with at least two of the following characteristics:
one sided location, pulsating quality, moderate or severe pain intensity, aggravation by routine physical activity
 - photophobia and phonophobia,
 - visual aura
- D. Not better accounted for by another vestibular or ICHD diagnosis

5.2 Exclusion Criteria

Exclusion criteria:

- (1) Previous SSNHL history
- (2) Previous middle ear disorder such as chronic otitis media, or previous ear surgery
- (3) Meniere's disease and fluctuating hearing loss patients
- (4) Pregnancy or trying to become pregnant
- (5) Leukemia, hemodialysis, and patients who received chemotherapy before.
- (6) Previous head and neck radiotherapy
- (7) CP angle tumor such as vestibular schwannoma
- (8) Patients with moderate to severe hepatic insufficiency
- (9) Patients with major depression disorder or suicide attempt
- (10) Patients with glaucoma

5.3 Withdrawal criteria

Withdraw from the study:

Participants of this study can withdraw from this study at any time when the patient disagree the consent, or had intolerable adverse effects after medication, or could not follow the treatment protocol.

The data of the withdraw patients will be excluded from the audiology analysis. The reason of withdrawal would be analyzed and reported.

6. Treatments

6.1.Treatment Administration

Both experimental group and control group will receive systemic steroid with/without intratympanic steroid as the standard treatment for sudden sensorineural hearing loss. The total duration of systemic steroid is 2 weeks.

As for the experimental group, topiramate 25 mg orally before bedtime with weekly escalation of 25 mg up to 100 mg. More specifically, the patient will receive 25mg daily at first week. Then the dose will be titrated up to 50mg in the second week, 75mg in the third week, and 100mg daily during the 4-6 weeks.

The dose of topiramate will be half in patients with renal insufficiency ($\text{Cl}_{\text{CR}} \leq 70 \text{ mL/min}$).

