0.80	0.80630	56	56	112	12.0	19.0	-7.0	13.0	0.050

References

Julious, S. A. 2010. Sample Sizes for Clinical Trials. Chapman & Hall/CRC. Boca Raton, FL.
Chow, S. C., Shao, J., and Wang, H. 2008. Sample Size Calculations in Clinical Research (Second Edition). Chapman & Hall/CRC. Boca Raton, FL.
Zar, Jerrold H. 1984. Biostatistical Analysis (Second Edition). Prentice-Hall. Englewood Cliffs, New Jersey.

Report Definitions

Target Power is the desired power value (or values) entered in the procedure. Power is the probability of rejecting a false null hypothesis.

Actual Power is the power obtained in this scenario. Because N1 and N2 are discrete, this value is often (slightly) larger than the target power.

N1 and N2 are the number of items sampled from each population.

N is the total sample size, $N1 + N2$.

μ_1 and μ_2 are the assumed population means.

$\delta = \mu_1 - \mu_2$ is the difference between population means at which power and sample size calculations are made.

σ is the assumed population standard deviation for each of the two groups.

Alpha is the probability of rejecting a true null hypothesis.

Summary Statements

Group sample sizes of 56 and 56 achieve 80.630% power to reject the null hypothesis of equal means when the population mean difference is $\mu_1 - \mu_2 = 12.0 - 19.0 = -7.0$ with a standard deviation for both groups of 13.0 and with a significance level (alpha) of 0.050 using a two-sided two-sample equal-variance t-test.

*Missing rate =10%, thus the enrollment size is 112/0.9=125

*Missing rate =20%, thus the enrollment size is 112/0.8=140

3. Efficacy assessment group : V Intent-to-treat (ITT) Per-Protocol (PP)
 Other _____
4. Interim analysis : Yes V No
5. Statistical methods : t test will be performed to compare pre- and posttreatment audiometric measurements. Chi-square and independent sample t test will be used to compare categorical and numerical variables between the two groups, respectively.
6. Handling of Missing Data : The cases with missing data will be omitted. The remaining data will be analyzed to determine the efficacy of study drug.

2. Introduction and Rationale

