11.3 Analysis Population

All eligible participants will be included in the analyses. If the participant wishes to withdraw due to any reason after enrollment, the data will also be reported.

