11.4 Procedure for accounting for missing, unused and spurious data

The incomplete clinical data and sequencing data with poor quality will be excluded in the study.

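### The protocol declares intention-to-treat but excludes withdrawn and incomplete patients from the hearing analysis, so it contradicts itself on who enters the primary comparison.

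*Protocol*

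**What the plan says.** Five statements in the protocol bear on who is analysed.

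- **Synopsis, Statistical Methods item 3** marks the efficacy set as "V Intent-to-treat (ITT"). Per-protocol is left unmarked.
- **Section 11.3**: "All eligible participants will be included in the analyses". On withdrawals it adds: "If the participant wishes to withdraw due to any reason after enrollment, the data will also be reported".
- **Section 5.3**: "The data of the withdraw patients will be excluded from the audiology analysis". The grounds for withdrawal are withdrawn consent, or that the patient "had intolerable adverse effects after medication, or could not follow the treatment protocol".
- **Synopsis, Statistical Methods item 6**: "The cases with missing data will be omitted".
- **Section 11.4**: "The incomplete clinical data and sequencing data with poor quality will be excluded in the study".

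The synopsis defines the primary endpoint as the improvement rate and gain in pure tone audiometry between day 0 and day 84. Section 4.2 plans 140 enrolled, 28 drop-outs and 112 evaluable ("experimental group 56, control group 56"). Section 4.3 schedules audiometry at day 0, day 56 and day 84.

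**The concern.** The primary endpoint is an audiology measure, so the section 5.3 exclusion acts directly on the primary test. That cannot stand beside an intention-to-treat declaration. Two analysts working from this protocol could analyse different patients and both claim to have followed it.

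Two features make this more than a labelling problem. First, the grounds for withdrawal include adverse effects and failure to follow treatment, and section 5.3 does not say whether a patient who only stops topiramate counts as withdrawn. Second, the trial is open label and only one arm takes topiramate, so losses may plausibly differ by arm. If they do, and if they relate to hearing, the completer comparison is biased in a direction that cannot be known in advance.

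A secondary point concerns section 4.1, which excludes patients later found to have another disease. Section 4.3 starts treatment at once while MRI or ABR is being arranged, so some of these exclusions can fall after randomisation.

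**Working it through.** **1. The passages side by side**

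| Place | Withdrawn patient with some audiometry | Patient with no day 84 value |
|---|---|---|
| Synopsis item 3 (ITT) | in | in |
| Section 11.3 | in if eligible; data reported | in if eligible |
| Section 5.3 | out | out if withdrawn |
| Synopsis item 6 | not addressed as such | out |
| Section 11.4 | out if incomplete | out |

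Section 11.3 does not settle the conflict, because reporting withdrawn patients' data is not the same as analysing them in the between-arm test. Under section 5.3, a patient who withdraws after the day 56 audiogram is removed even from the day 56 secondary endpoint.

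**2. The plan's own figure**

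Inputs from the synopsis: difference 19 − 12 = 7 dB, SD 13, two-sided alpha 0.05, equal-variance t test, 56 per arm. (Section 11.1 names 5 dB for the same size; that is a separate matter, and 7 dB is used here.)

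SE = 13 × √(1/56 + 1/56) = 2.457. The noncentrality is 7/2.457 = 2.849, and power from the noncentral t is 80.6%, which matches the synopsis. Enrolment is 112/0.8 = 140, so 28 (20%) may be lost. The stated power therefore belongs to the 112 who remain.

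**3. Possible bias if completers are compared**

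Within an arm, completer mean − all-randomised mean = (fraction lost) × (gain in kept − gain in lost). With the same gap in both arms:

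bias = (lost in topiramate/70 − lost in control/70) × gap.

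The splits and gaps below are assumptions; the documents give none. Positive bias favours topiramate.

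No true effect, lost patients gain 5 or 10 dB less than kept patients:

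| Lost (topiramate/control) | Analysed | Gap | Bias | False-positive rate |
|---|---|---|---|---|
| 14/14 | 56/56 | 5 or 10 dB | 0 | 5.0% |
| 18/10 | 52/60 | 5 dB | (8/70) × 5 = 0.57 dB | 5.6% |
| 18/10 | 52/60 | 10 dB | (8/70) × 10 = 1.14 dB | 7.5% |
| 21/7 | 49/63 | 5 dB | (14/70) × 5 = 1.0 dB | 6.9% |
| 21/7 | 49/63 | 10 dB | (14/70) × 10 = 2.0 dB | 12.6% |

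Reversed sign (lost patients gain 5 or 10 dB more, for example because recovered patients stop attending), with a true 7 dB effect:

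| Lost (topiramate/control) | Expected difference | Power |
|---|---|---|
| 18/10 | 7 − 0.57 = 6.43 dB; 7 − 1.14 = 5.86 dB | 73%; 65% |
| 21/7 | 7 − 1 = 6 dB; 7 − 2 = 5 dB | 67%; 52% |

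**4. Power if everyone is analysed as assigned**

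Assume a fraction of the topiramate arm gains no added benefit, so that the expected difference is 7 × (1 − fraction).

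| Fraction without benefit | Difference | 70 per arm | 63 per arm (10% still missing) |
|---|---|---|---|
| 0 | 7.0 dB | 88.6% | 85% |
| 10% | 6.3 dB | 81% | 77% |
| 20% | 5.6 dB | 72% | 67% |
| 30% | 4.9 dB | 60% | 56% |

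**The case against.** The strongest reply is that the plan is mislabelled rather than ambiguous. Section 5.3, synopsis item 6, section 11.4 and the step from 140 to 112 all point to completers. Against them stand only a tick-box and one general sentence. This is fair as a guess at intent, but it concedes the point: the declared set and the operative rules disagree. A completer set that drops patients for adverse effects or non-adherence is close to per-protocol.

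A second reply is that leaving out a patient with no day 84 audiogram is a missing-data method, not an exclusion of observed data. That stands for synopsis item 6. It does not cover section 5.3, which discards withdrawn patients whatever audiometry they have. Section 11.4 is also weak support, since it mentions sequencing data that this trial does not otherwise describe.

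Third, the 28 is a planning allowance that combines incomplete data with drop-out, and many of those patients might have no day 84 value under any rule. This stands: the number with usable audiometry that section 5.3 would discard is unknown and could be small. The assumed splits and gaps show what could happen; they do not estimate it.

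Fourth, section 5.3 is permissive: patients may withdraw, and nothing orders the removal of non-adherent patients. This is true, but it leaves the status of a topiramate discontinuer open, which is part of the problem.

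Finally, MRI or ABR and randomisation share the screening column and 10 screening failures are budgeted, so exclusions after randomisation under section 4.1 may be few. That point is accordingly secondary.

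**Conclusion.** The concern holds and must be fixed before analysis. The protocol gives incompatible rules for the primary analysis set, and this does not depend on any assumed pattern of loss. An SAP could resolve it only by overriding one protocol statement in favour of another.

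Up to 28 of 140 patients (20%) are affected. The resulting bias cannot be estimated from the documents. It is zero with balanced loss and equal gaps, or with loss unrelated to hearing. Under the assumed unequal splits and 5 to 10 dB gaps it runs from 0.6 to 2 dB in either direction. That means a false-positive rate of up to 12.6% when there is no effect, or power as low as 52% for a true 7 dB effect.

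**What to change.** 1. **Section 5.3 (main remedy).** Replace the exclusion sentence. Patients who stop study drug or deviate from treatment should stay in the study, have the day 56 and day 84 audiometry unless they withdraw consent for it, and be analysed in the arm assigned. Follow-up matters most because a patient lost before day 56 has no scheduled post-baseline audiogram, and modelling from day 0 adds little for such a patient.
2. **Synopsis items 3 and 6, sections 11.3 and 11.4.** Align them with this rule. Section 11.3 should say that withdrawn patients' available data are analysed, not only reported.
3. **Missing data.** Replace case deletion with an analysis of all randomised patients that uses the available day 0 and day 56 values, leaving the method to the SAP. Add a sensitivity analysis over a range of assumed gains by arm for patients with no post-baseline audiogram. Keep complete cases as supportive.
4. **Section 4.1 (secondary).** Limit the later exclusion to ineligibility shown by the day 0 work-up and judged without knowledge of arm.

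The cost is protocol and SAP wording, plus the effort of bringing back patients who have stopped; no visits are added. The effect may be diluted: with 70 per arm, power stays above 80% if 10% of the topiramate arm gain no added benefit, but falls to 72% at 20% and 60% at 30%. The sample size should be rechecked against the dilution expected.
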